5.5 Criteria for Temporarily Delaying

Due to the logistics of group therapy, there must be adequate flexibility factored into the timing of screening and enrollment. In order to construct a group cohort of six individuals, the study team must recruit and screen enough potentially eligible participants for a group cohort within a relatively short timeframe, consider appropriate distribution of individual factors during the group cohort selection process (as described in [Section 5.6 Recruitment Strategies](#) below), coordinate schedules among group members and participating staff members, and coordinate multiple medication taper plans and assessments. The timing of enrollment for individual participants may be delayed (e.g., to another group cohort that may better suit the individual) or adjusted at the investigator’s discretion in order to achieve the same group start date (Preparatory Session 1) for the full cohort.

5.6 Recruitment Strategies

Recruitment efforts will focus on an enrollment target of six participants per group therapy cohort. Thus, study staff will need to concentrate enough screening assessments within a given enrollment period. Furthermore, group cohorts will be planned with considerations of veterans’ service era (e.g., OEF/OIF, Vietnam), type of trauma (e.g., military-related trauma, combat-related, military sexual trauma), and gender identity to facilitate group cohesion. The optimal number and diversity of participants making up each group cohort will be flexible and adaptable and informed by earlier cohorts.

6.0 Study Intervention(s) and Concomitant Therapy

Study intervention is defined as any investigational intervention(s), marketed product(s), placebo, or medical device(s) intended to be administered to a study participant according to the study protocol.

6.1 Study Intervention(s) Administered

6.1.1 Medications

The Active Pharmaceutical Ingredient (API) to be used in this protocol is MDMA as a hydrochloride salt (HCl). Refer to the IB for a comprehensive review of the pharmacology, effects, and proposed mechanisms of action of the Investigational Medicinal Product (IMP).

Table 3: Study Medication Intervention Administered

Intervention Label	Active Intervention
Intervention Name	3,4-methylenedioxymethamphetamine (MDMA) as a hydrochloride salt (HCl)
Intervention Description	Initial doses per Experimental Session include 100 mg MDMA, followed 1.5 to 2 hours later by a supplemental dose of 34 or 50 mg MDMA (equivalent to 120 mg followed by 40 or 60 mg MDMA HCl).
Type	drug
Dose Formulation	capsule
Unit Dose Strength(s)	34 or 50 mg MDMA (equivalent to 40 or 60 mg MDMA HCl)
Dosage Level(s)	Initial: 100 mg MDMA (equivalent to 120 mg MDMA HCl) Supplemental: 34 mg or 50 mg MDMA (equivalent to 40 mg or 60 mg MDMA HCl)
Route of Administration	Oral
Use	Experimental
IMP and NIMP/AxMP.	IMP
Sourcing	Provided centrally by the sponsor.
Packaging and Labeling	Each package will be an open-label container that will be used as bulk presentation at the study site and labeled as required per federal, state, and local regulations. This will include the following: Caution: New Drug-Limited by Federal (or United States) law to investigational use.

6.1.1.1 Preparation, Handling, Storage, and Accountability

The investigator or designee must confirm appropriate temperature conditions have been maintained during transit for all study IMP received, and any discrepancies are reported and resolved before use of the study IMP.

Only participants enrolled in the study may receive study intervention, and only authorized site staff may supply or administer study IMP. All IMP must be stored in a secure, environmentally controlled, and monitored (manual or automated) area in accordance with the labeled storage conditions with access limited to the investigator and authorized site staff.

The investigator, institution, or the head of the medical institution (where applicable) is responsible for study IMP accountability, reconciliation, and record maintenance (i.e., receipt, reconciliation, and final disposition records).

Further guidance and information for the final disposition of unused IMP are provided in the Pharmacy Manual.

6.2 Therapy

6.2.1 Description of Therapeutic Model

The largely non-directive therapeutic method of MDMA-assisted therapy is described in detail in the Treatment Manual. All therapy teams will be extensively trained through the MDMA Therapy Training Program prior to the study to ensure all participants are treated in a similar manner. The non-directive approach pertains to inviting inquiry and providing suggestion rather than directing the participant in the therapeutic approach. This requires active or engaged listening and responding, as well as facilitation of therapeutic action by providing support for approaching difficult material in a manner that does not interfere with the participant's spontaneous experience.

6.2.2 Implementation of a Therapeutic Model in a Group Setting

Each individual session (Individual Preparation, Experimental, and Integration Sessions) will be conducted according to the existing Treatment Manual with the same two-person therapy pair across sessions for each individual participant. Therapy pairs may be termed "co-facilitators" in this group protocol to reflect with standard group therapy terminology. Group Preparatory and Integration Sessions will be conducted by two co-facilitators and will incorporate a group therapy model. Four co-facilitators will be assigned to each group cohort of six participants. During the Group Experimental Session, all four co-facilitators will be present. Participants will be extensively prepared for the inner-directed approach to the Group Experimental Session. During the Group Experimental Session, participants will primarily be engaged in their own internal experience, interacting with their assigned facilitator(s) as needed; group processing will be reserved for before MDMA ingestion and toward the end of the session.

6.2.3 Therapy Team Qualifications

Therapy teams will be trained by the sponsor. Sites must ensure that the minimum requirements below are met:

- One or more two-person therapy pairs (co-facilitators), who have been reviewed and approved by the MDMA Therapy Training Program.
- One person per therapy team pair is required to be licensed to provide therapy according to state or province and local requirements.
- If one person on the therapy team is unlicensed, they will be required to have, at a minimum, a bachelor's degree and either be trained in mental health (including students in a postgraduate internship-type program providing detailed knowledge of mental health interventions and treatments) or have completed 1000 hours of behavioral health experience prior to co-facilitating sessions as a part of a co-pair.

A physician will be required to be on the study team to assess participant safety. Each site will also be required to have one person licensed to manage and administer controlled substances.

6.2.4 Therapy Training Program

The MDMA Therapy Training Program is designed to teach competency in applying the essential elements of this method of MDMA-assisted therapy. Therapy team members will receive specific training in the MDMA-assisted therapy method, protocol, and latest version of the IB. Training in the therapy method consists of reading the Treatment Manual, completing online training modules, and participating in an in-person or online training that includes watching and

discussing videos of Experimental Sessions. The required elements of the therapy are defined in the Treatment Manual, and teams will be trained on visit-specific sets of adherence criteria. In addition to this specific training, it is required that participating therapy team members have the proper background, education, and experience.

6.2.5 Adherence to Therapeutic Method

Therapy sessions, including Experimental Sessions, may be recorded, with recordings preserved for research and training purposes. Adherence ratings will be conducted by qualified, trained, and reliable adherence raters who will analyze video data from specific Preparatory Sessions, Experimental Sessions, and Integrative Sessions conducted with individual participants. The elements included in adherence criteria are specific to each type of session and are defined in the Adherence Manual. These ratings will be collected, at minimum, for each therapy team in the study. Ratings will be used to provide feedback to new therapy teams, to further characterize the manualized therapy, and for future exploratory research. In addition to adherence ratings of sessions conducted with individual participants, specific group-level Preparatory, Experimental, and Integrative sessions will be reviewed by Adherence Raters. As the adherence criteria for MDMA-assisted therapy for PTSD have been developed to identify adherence in sessions with an individual participant, Adherence Raters will qualitatively evaluate group sessions for adherence to the non-directive approach, providing written commentary identifying areas of accord or variation from the extant adherence criteria.

6.3 Measures to Minimize Bias

Participants, site staff, and the sponsor will be aware that each participant will be receiving open-label MDMA with no blinding at the site level. To minimize bias in measuring effectiveness, the sponsor will use an observer-blind, centralized, reliable IR pool to administer the Primary Outcome measure via tele-assessment. The IR Pool will have no knowledge of participant's study data or AEs and will only evaluate participants at Baseline and at the assessments scheduled after each Experimental Session. The IR Pool is blinded to study design, visit number, number of treatments, and any data from the treating therapy team after Baseline. IRs will be assigned to participants based on availability.

To ensure that all participants are treated in a similar manner, the site will be required to follow the protocol and Treatment Manual delineating minimum length of time per visit type and describing delivery of treatment. All Experimental Sessions are required to be at least 6 hours long. Adherence to the Treatment Manual will be checked by review of video by adherence raters. The sponsor will monitor data in real-time to ensure complete data collection for all participants, including those who discontinue treatment. Sites will be required to make and document a specific number of attempts to obtain follow-up data per protocol. All participants who receive at least one dose of IMP and complete at least one follow-up assessment will be included in the final mITT analysis.

Type of Study	
Open-label, no blinding at site level	This is an open-label study; potential bias will be reduced by the following steps: use of blinded, centralized, Independent Raters to assess baseline and outcome measure.

6.4 Study Intervention Compliance

When the individual dose for a participant is prepared from a bulk supply, the preparation of the dose will be confirmed by a second member of the study site staff.

When participants are dosed at the site, they will receive study IMP directly from the investigator or designee. The date and time of each dose administered will be recorded in the source documents. The dose of IMP and study participant identification will be confirmed at the time of dosing by a member of the study site staff other than the person administering the study intervention.

6.5 Dose Modification

In each Experimental Session, 1.5 to 2 hours after the initial dose is given, the participant will be administered a supplemental dose unless tolerability issues emerge or the participant declines, in which case no supplemental dose will be administered.

6.6 Continued Access to Study Intervention after the End of the Study

After completion of the study, no further access to the study intervention (IMP or therapy) will be provided. Participants will work with their therapy team to identify future plans for therapy and support as described in [Section 8.4.4 Plan Moving Forward](#).

6.7 Treatment of Dosing Errors

For this study, any dose of MDMA greater than intended dose of study intervention within a 24-hour time period will be documented as a dosing error.

In the event of a dosing error, the investigator/treating physician should:

- Contact the Medical Monitor immediately.
- Closely monitor the participant for any AE/SAE.
- Document the quantity of the dosing error.

6.8 Concomitant Therapy

Any medication or vaccine (including over-the-counter or prescription medicines, recreational drugs, vitamins, and/or herbal supplements) that the participant is receiving at the time of enrollment or receives during the study must be recorded along with:

- Reason for use
- Dates of administration including start and end dates
- Dosage information including dose and frequency

Participants must abstain from taking prescription or nonprescription drugs (including vitamins, recreational drugs, and dietary or herbal supplements) within 7 days (or 14 days if the drug is a potential enzyme inducer) or 5 half-lives (whichever is longer) before the start of study intervention until completion of the follow-up visit, unless, in the opinion of the investigator and sponsor, the medication will not interfere with the study.

The Medical Monitor should be contacted if there are any questions regarding concomitant or prior therapy.

6.8.1 Psychiatric Medications

Psychiatric medications approved for treatment of PTSD, are under investigation for treatment of PTSD, or which are used off-label to treat symptoms of PTSD are not permitted during the trial and must be tapered during the Preparatory Period. If the participant is being treated with any such medication(s) at enrollment, the participant will be encouraged to discuss medication tapering with their outside treating physician and will be required to give the site physician permission to do so as well. The medications will then be tapered in an appropriate fashion to avoid withdrawal effects and discontinued at least five half-lives plus one additional week for stabilization before Baseline to avoid the possibility of any interaction.

The site physician will consult the prescribing physician to initiate medication tapering for participants, as they must refrain from taking psychiatric medications throughout the study, with some exceptions, see [Section 6.8.2 Permitted Concomitant Medications](#). The prescribing physician's opinion about medication discontinuation should be documented in the participant's study record. Tapering will follow a time course appropriate for the medication based on its half-life, with Baseline scheduled to occur after complete washout (five half-lives plus at least 1 week for stabilization). If the health of the participant worsens after tapering, the participant will be withdrawn from the study and will be treated according to standard clinical practice. This will be recorded in the eCRF.

The therapy team will request information about any changes in medication at each contact. The site physician will be responsible for reviewing and confirming all medications collected during the study.

All medications, non-prescription and prescription, will be collected from Screening through 7 days after the last Experimental Session. From 7 days after the last Experimental Session through Study Termination, only prescription or non-prescription medications taken to treat AEs will be collected. Throughout the protocol, all medications used to treat AEs will be collected, and all changes including discontinuations or additions to medications will be collected. The study team will inquire and document all information about withdrawal and tapering of medications, concomitant medication, and medication adherence in the eCRF Concomitant Medications.

Participants may return to taking psychiatric medications and discontinue study-required contraception methods after the final Study Termination visit if necessary.

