5.1 Inclusion Criteria

Participants are eligible to be included in the study only if all the following criteria apply:

Age

1. Be 18 years of age at the time of signing the informed consent.

Type of Participant and Disease Characteristics

2. Are a military veteran.
3. At Screening, meet DSM-5 criteria for current PTSD
4. Fluent in speaking and reading the predominantly used or recognized language of the study site.
5. Able to swallow pills.
6. Agree to have study visits video-recorded, including Experimental Sessions, IR assessments, and non-drug therapy sessions.
7. Able to identify appropriate support person(s) to stay with the participant on the evening of the Experimental Session, see [Section 8.2.4 Support Person](#).
8. Able to provide a contact (relative, spouse, close friend, or other support person) who is willing and able to be reached by the investigators in the event of the participant becoming unwell or unreachable.
9. Agree to inform the investigators within 48 hours of any medical conditions and procedures.

Weight

10. Body weight of at least 48 kilograms (kg).

Sex and Contraceptive/Barrier Requirements

11. For participants assigned female sex at birth:
 - A participant is eligible to participate if not pregnant or breastfeeding, and one of the following conditions applies:
 - Is not able to become pregnant as defined in [Appendix 2: Contraceptive and Barrier Guidance](#).
 - OR
 - Is a person able to become pregnant (PABP) and using a contraceptive method that is highly effective, with a failure rate of <1%, as described in [Appendix 2: Contraceptive and Barrier Guidance](#), during the study intervention period and for at least 10 days after the last dose of study intervention. The investigator should evaluate the potential for contraceptive method failure (e.g., noncompliance, recently initiated) in relationship to the first dose of study intervention.
 - A PABP must have a negative highly sensitive pregnancy test (urine or serum as required by local regulations) at study entry and prior to each experimental session.
 - The investigator is responsible for review of medical history, menstrual history, and recent sexual activity to decrease the risk for inclusion of a participant with an early undetected pregnancy.

Informed Consent

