7.1 Discontinuation of Study Intervention

In rare instances, it may be necessary for a participant to permanently discontinue study intervention. If study intervention is permanently discontinued, the participant may remain in the study and continue with remaining individual sessions, but will not participate in any further group therapy sessions. If the investigator determines it is in the participant's best interest to completely withdraw from the study, an early discontinuation visit should be conducted..

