7.2 Participant Discontinuation/Withdrawal from the Study

- A participant may withdraw from the study at any time at their own request or may be withdrawn at any time at the discretion of the investigator for safety, behavioral, or compliance reasons. This is expected to be uncommon.
- At the time of discontinuing from the study, if possible, an early discontinuation visit should be conducted..
- The participant will be permanently discontinued from the study intervention and the study at that time. The site team will provide the participant with a plan moving forward as described in [Section 8.4.4 Plan Moving Forward](#).
- If a participant develops any Exclusion Criteria that, in the opinion of the Medical Monitor or Site, affects the safety of the participant, the participant will discontinue treatment in Experimental Sessions but may remain in the study for any individual associated non-drug Therapy and Integrative Sessions.
- If a participant withdraws consent for disclosure of future information, the sponsor may retain and continue to use any data collected before such a withdrawal of consent.

- If a participant withdraws from the study, they may request destruction of any samples taken and not tested, and the investigator must document this in the site study records.
- If a participant withdraws, cohort will continue with reduced size.

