8.3.3 Integrative Sessions

After each Experimental Session, four Integrative Sessions will take place. Each session will consist of 90 minutes of therapy.

On the morning after the Experimental Session, the participants will be escorted to the study site via car, rideshare, or public transportation, as participants are not allowed to drive within 24 hours of administration of MDMA.

In addition to completing the study procedures, the therapy team will discuss and review events that occurred with the participant during the Experimental Session, including thoughts, feelings, and memories. If necessary, the therapy team will help the participants to reduce any residual psychological distress they are experiencing. The therapy teams will also encourage the transfer of states of acceptance, feelings of intimacy, closeness, and reduced fear experienced in Experimental Sessions to emotionally threatening everyday situations. The therapy teams will be supportive, validate the experience, and facilitate understanding and emotional clearing.

Table 7: Integration Sessions after Experimental Sessions

Following First Experimental Session		
Visit	Individual or Group	Visit Timing
Integration Session 1.1	Individual	Morning after Experimental Session 1
Integration Session 1.2	Group	~1 week (3-14 days) after Experimental Session 1
Integration Session 1.3	Group	~2 weeks (10-21 days) after Experimental Session 1
Integration Session 1.3	Group	~3 weeks (17-28 days) after Experimental Session 1; 1-7 days before Experimental Session 2
Following Second Experimental Session		
Integration Session 2.1	Group	Morning after Experimental Session 2
Integration Session 2.2	Group	~1 week (3-14 days) after Experimental Session 2
Integration Session 2.3	Group	~2 weeks (10-21 days) after Experimental Session 2
Integration Session 2.4	Group	~3 weeks (17-28 days) after Experimental Session 2

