8.4.2 Independent Rater Final Assessment

Participants will have a final Outcome assessment at the completion of the follow-up period. An IR will conduct the assessments via tele-assessment. These assessments may be recorded to establish inter-rater reliability. The results may be shared with site staff during supervision by the therapy training team. Participants who have withdrawn from treatment will also complete a final

Outcome assessment immediately upon withdrawal. The IR will also administer the SDS and DSP-I.

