8.4.3 Study Termination

Study Termination will take place 1 week (0-9 days) after the final CAPS-5 assessment and can occur on the same day as Outcome visit. Participants who have withdrawn from treatment but have continued for follow-up will also complete this assessment immediately upon withdrawal.

After all Study Termination measures and assessments are completed, the participant is considered terminated from the study. The participant can resume normal everyday life. The study team will provide a plan moving forward, which may include a referral for additional medical or therapeutic care, as described in [Section 8.4.4 Plan Moving Forward](#). Eligible participants may be invited to participate in a future long-term follow-up (LTFU) extension study, which will be conducted under a separate protocol.

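### Section 6.8.1 ties the end of contraception to the Study Termination visit, which for a participant withdrawn from treatment can fall inside the 10-day post-dose minimum of criterion 11.

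*Protocol*

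**What the plan says.** Section 5.1, criterion 11, counts from the dose. A participant able to become pregnant must use highly effective contraception "during the study intervention period and for at least 10 days after the last dose of study intervention".

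Section 6.8.1 counts from a visit. Its closing sentence lets participants "discontinue study-required contraception methods after the final Study Termination visit if necessary". It gives no time since dosing and does not refer to criterion 11. Appendix 2 lists acceptable methods but no post-dose duration.

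The timing of that visit depends on how the participant leaves treatment:

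- Section 8.4.3, general rule: "Study Termination will take place 1 week (0-9 days) after the final CAPS-5 assessment and can occur on the same day as Outcome visit".
- Section 8.4.2: those withdrawn from treatment have the final "Outcome assessment immediately upon withdrawal".
- Section 8.4.3, same group: "Participants who have withdrawn from treatment but have continued for follow-up will also complete this assessment immediately upon withdrawal".
- Section 7.1: a participant whose study intervention is permanently discontinued "will not participate in any further group therapy sessions".
- Section 7.2, for those leaving the study altogether: "At the time of discontinuing from the study, if possible, an early discontinuation visit should be conducted".

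**The concern.** The two contraception rules agree only if Study Termination always falls at least 10 days after the last dose. Nothing in the protocol guarantees that for participants withdrawn from treatment soon after dosing. Section 6.8.1 is the only text that says when contraception may stop, so site staff closing out such a participant would find a permission to stop and no reminder of the 10 days.

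Table 1 in Section 2.3.1 acknowledges that there are no clinical data on MDMA in pregnancy, and the 10-day minimum is the protocol's own choice. Section 8.7.9 collects pregnancy details only up to the participant's final visit. A conception after that visit but still within 10 days of the dose would therefore fall outside routine collection.

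**Working it through.** No sample size, power or error rate is involved. The check is calendar arithmetic on the visit windows.

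**Completers.** Days from the last dose (Experimental Session 2) to Study Termination are the sum of three windows:

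- Session 2 to Integration Session 2.4: 17 to 28 days (Table 7).
- Follow-up after Session 2.4: 4 weeks ± 2 weeks, so 14 to 42 days (Section 8.4.1).
- Final CAPS-5 to Study Termination: 0 to 9 days (Section 8.4.3).

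Earliest: 17 + 14 + 0 = 31 days. Latest: 28 + 42 + 9 = 79 days. Even the earliest exceeds the 10-day minimum by 31 − 10 = 21 days.

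**Participants withdrawn from treatment.** Let w be the day of withdrawal, counted from the last dose. Let s be the number of days from withdrawal, with a same-day Outcome assessment, to Study Termination. Then

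shortfall against criterion 11 = max(0, 10 − w − s).

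Section 8.4.3 allows s from 0 to 9, with one week as the nominal value.

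| s (days) | Withdrawal days with a gap | Shortfall |
|---|---|---|
| 0 | 0 to 9 | 10 days at w = 0; 9 at w = 1; 3 at w = 7; 1 at w = 9; none at w = 10 |
| 7 | 0 to 2 | 3, 2 and 1 days at w = 0, 1 and 2; none at w = 3 |
| 9 | 0 only | 1 day; none at w = 1 |

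**Does a scheduled session hold the visit back to day 10?** No. Under Section 7.1 the group sessions end when the intervention is permanently discontinued. Table 7 lists one individual integration session, 1.1, timed "Morning after Experimental Session 1". All four sessions after Experimental Session 2 are group sessions. The gap can therefore follow either dose.

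**Participants who leave the study altogether.** They have an early discontinuation visit under Section 7.2. Section 6.8.1 names only Study Termination, so its permission is not triggered and criterion 11 alone governs them.

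**Pharmacological scale.** Section 2.2.3 gives a half-life of 7 to 9 hours. Five half-lives take 5 × 7 = 35 to 5 × 9 = 45 hours. Ten days is 240 hours, which is 240/9 = 26.7 to 240/7 = 34.3 half-lives.

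**The case against.** The strongest reply is that the two rules are cumulative. Criterion 11 sets the requirement, criterion 12 binds participants to the restrictions in the consent form and the protocol, and the sentence in 6.8.1 is a permissive remark in a section about psychiatric medication. On that reading a participant must satisfy both the 10 days and the visit. This reading is possible. But 6.8.1 does not state it, and criterion 11 is an entry criterion that staff are unlikely to consult at close-out.

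A second reply is that Sections 8.3 and 8.3.2 schedule telephone calls every other day for 14 days after each Experimental Session, and that 8.4.3 speaks of those who continued for follow-up, which fits poorly with termination in the first days. The wording of 8.4.3 is awkward, and a later Study Termination can be read into it. However, nothing makes Study Termination wait for the calls. Even without that sentence, 8.4.2 places the Outcome assessment immediately upon withdrawal and the general rule in 8.4.3 allows Study Termination the same day.

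Third, Section 8.6.6 asks for a pregnancy test at the end of relevant systemic exposure. That can detect a pregnancy but does not extend contraception.

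Fourth, the Schedule of Activities and the consent form are not in the text at hand, and either may carry the 10-day rule. This caveat stands.

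Finally, the practical weight is slight. That also stands, and it sets the priority of the point.

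**Conclusion.** The concern holds as a narrow inconsistency in a safety rule. As written, 6.8.1 can release a participant withdrawn from treatment up to 10 days before the protocol's own minimum has run. The size depends on how soon Study Termination follows withdrawal: with a same-day visit the gap exists for withdrawal on days 0 to 9, and with the nominal one-week interval only on days 0 to 2. Completers are not affected.

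The conclusion assumes a same-day Outcome assessment, as 8.4.2 directs, and that no 10-day rule appears in the Schedule of Activities. The protocol gives neither the number of participants able to become pregnant nor the number expected to withdraw from treatment early. Section 7.2 expects withdrawal from the study to be uncommon, so probably none or very few of the 18 would be affected. Since five half-lives pass in under two days, the pharmacological risk is very small. This is a point to consider, not a serious defect.

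**What to change.** In Section 6.8.1, allow study-required contraception to stop only at the later of (a) the final study visit, whether Study Termination or early discontinuation, and (b) 10 days after the last dose actually received. Naming the early discontinuation visit puts every route out of the study under one rule. Counting from the dose actually received covers a participant whose only dose was in Experimental Session 1.

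The cost is one clause. It needs no new visit, test or call, no other section has to change, and nothing changes for completers. A participant withdrawn with immediate Study Termination on day 1 would continue contraception for 9 more days, and one on day 7 for 3 more. If the Schedule of Activities already states the 10-day rule, a cross-reference to it in 6.8.1 is sufficient.
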